7.4 Return product analysis

Alcon products associated with device deficiencies and/or product related AEs should be returned and must include the Complaint # which will be provided by Study Sponsor after the case is entered in the Study Sponsor's Global Product Complaint Management System. These products should be returned to the Sponsor at the end of the study, unless instructed otherwise by the Sponsor.

7.5 Follow-up of Subjects with Adverse Events

The Investigator is responsible for adequate and safe medical care of subjects during the study and for ensuring that appropriate medical care and relevant follow-up procedures are maintained after the study.

The Investigator should provide the Study Sponsor with any new safety information (which includes new AEs and changes to previously reported AEs) that may affect the safety evaluation of the device. For AEs that are unresolved/ ongoing at time of subject exit from study, any additional information received at follow-up should be documented in the eCRFs up to study completion (ie, database lock).

Any additional data received up to 1 month after subject discontinuation or exit must be documented and available upon the Study Sponsor's request. All complaints received after this time period will be considered and processed as spontaneous and should be communicated to the medical device's manufacturer as per local requirements.

The Investigator should also report complaints on non-Alcon products directly to the manufacturer as per the manufacturer's instructions or local regulatory requirements.

7.6 Pregnancy in the Clinical Study

Women of childbearing potential or women who are pregnant at the time of study entry are not excluded from participation. Pregnancy should be included in the Medical History section of the eCRF when a pregnant woman enters the study or if a woman becomes pregnant during the study. Pregnancy is not reportable as an AE; however, complications may be reportable and will be decided on a case-by-case basis.

8 CONFIDENTIALITY, BIAS, AND MASKING

8.1 Subject Confidentiality and Methods Used to Minimize Bias

The Investigator must ensure that the subject's anonymity is maintained throughout the course of the study. In particular, the Investigator must keep an enrollment log with

confidential identifying information that corresponds to the subject numbers and initials of each study participant. At the end of the clinical study, the Sponsor will collect a copy of the enrollment log without any identifying subject information. All documents submitted to the Sponsor will identify the subjects exclusively by number and demographic information. No other personally identifying information should be transmitted to the Sponsor.

This study is double-masked with subjects randomized to use both DD T2 and the assigned control product (in a randomized sequence) for the duration of the treatment period. The Investigator and Sponsor personnel (other than site monitors, lead clinical site manager, person responsible for generating the randomization schedule, and unmasked clinical data managers) involved in reporting, obtaining, and/or reviewing the clinical evaluations will be masked to the identity of the contact lens being administered. This level of masking will be maintained throughout the conduct of the study. Unmasking will occur only after all planned study data have been validated, and the database locked. Masked study personnel must avoid seeking information that may compromise masking. Unmasked study personnel must not disseminate information that is potentially unmasking to any masked personnel. The **masked** and **unmasked** site personnel must coordinate all study activities as necessary to protect masking and minimize bias during the trial.

8.2 Unmasking of the Study Treatment

Masked information on the identity of the assigned medical device should not be disclosed during the study. If the treatment code needs to be broken in the interest of subject safety, the Investigator is encouraged to contact an appropriate Study Sponsor representative prior to unmasking the information if there is sufficient time. Dependent upon the individual circumstances (ie, medical emergency), the code may be broken prior to contact with the Study Sponsor. The Study Sponsor must be informed of all cases in which the code was broken and of the circumstances involved. Additionally, the Study Sponsor may be required to unmask the information in order to fulfill expedited regulatory reporting requirements.

9 DATA HANDLING AND ADMINISTRATIVE REQUIREMENTS

9.1 Completion of Source Documents and Case Report Forms

The nature and location of all source documents will be identified to ensure that original data required to complete the eCRFs exist and are accessible for verification by the site monitor, and all discrepancies shall be appropriately documented via the query resolution process. Study monitors are appointed by the Study Sponsor and are independent of study site staff. If electronic records are maintained, the method of verification must be determined in advance of starting the study.

At a minimum, source documents should include the following information for each subject:

- Subject identification (name, sex, race/ethnicity)
- Documentation of subject eligibility
- Date of informed consent
- Dates of visits
- Documentation that protocol specific procedures were performed
- Results of study parameters, as required by the protocol
- IP accountability records
- Documentation of AEs and other safety parameters (if applicable)
- Records regarding medical histories and the use of concomitant therapies prior to and during the study
- Date of study completion and reason for early discontinuation, if applicable

It is required that the author of an entry in the source documents be identifiable. Direct access to source documentation (medical records) must be allowed for the purpose of verifying that the data recorded on the eCRF are consistent with the original source data.

Only designated individuals may complete the eCRFs. The eCRFs will be submitted at regular intervals following the clinical study visit schedule. It is expected that all data reported will have corresponding entries in the source documents. The Principal Investigator is responsible for reviewing and certifying that the eCRFs are accurate and complete. The only subject identifiers recorded on the eCRFs will be subject number, and subject demographic information.

9.2 Data Review and Clarifications

Upon completion of the eCRFs, a targeted review of the eCRF data to the subject's source data will be completed by the site monitor to ensure completeness and accuracy. Additional data clarifications and/or additions may be needed as a result of the data cleaning process. Data clarifications are documented and are part of each subject's eCRFs.

9.3 Regulatory Documentation and Records Retention

The Investigator is required to maintain up-to-date, complete regulatory documentation as indicated by the Sponsor and the Investigator's files will be reviewed as part of the ongoing

study monitoring. Financial disclosure is not subject to regulatory inspection and should be kept separately.

Additionally, the Investigator must keep study records and source documents until the Sponsor provides written approval for their destruction. If the Investigator retires, relocates, or for any other reason withdraws from responsibility of keeping the study records, the Sponsor must be notified and suitable arrangements made for retention of study records and source documents needed to comply with national and international regulations (generally 2 years after discontinuing clinical development or after the last marketing approval).

10 ETHICS AND COMPLIANCE

This trial will be conducted in accordance with the ethical principles that have their origin in the Declaration of Helsinki and the referenced directives, regulations, guidelines, and/or standards.

10.1 Compliance

The Investigator must ensure that all personnel involved in the conduct of the study are qualified to perform their assigned responsibilities through relevant education, training, and experience. The Investigator and all clinical study staff must conduct the clinical study in compliance with the protocol. Deviations from this protocol, regulatory requirements and/or GCP must be recorded and reported to the Sponsor prior to database lock. If needed, corrective and preventive action should be identified, implemented, and documented within the study records.

10.2 Institutional Review Board (IRB)

This trial requires IRB approval prior to initiation. This protocol, subject informed consent, and subsequent amendments will be reviewed and approved by an IRB.

Before clinical study initiation, this protocol, the ICF (and assent form, if applicable), any other written information given to subjects, and any advertisements planned for subject recruitment must be approved by an IRB. The Investigator must provide documentation of the IRB approval to the Study Sponsor. The approval must be dated and must identify the applicable protocol, amendments (if any), ICF, assent form (if any), all applicable recruiting materials, written information for subject, and subject compensation programs. The IRB must be provided with a copy of the Investigator's Brochure, any periodic safety updates, and all other information as required by local regulation and/or the IRB. At the end of the study, the Investigator must notify the IRB about the study's completion. The IRB also must be notified

if the study is terminated prematurely. Finally, the Investigator must report to the IRB on the progress of the study at intervals stipulated by the IRB.

Voluntary informed consent must be obtained from every subject (and/or legal representative, as applicable) prior to the initiation of any screening or other study-related procedures. The Investigator must have a defined process for obtaining consent. Specifically, the Investigator, or delegate, must explain the clinical study to each potential subject and the subject must indicate voluntary consent by signing and dating the approved informed consent form. The subject must be provided an opportunity to ask questions of the Investigator, and if required by local regulation, other qualified personnel. The Investigator must provide the subject with a copy of the consent form written in a language the subject understands. The consent document must meet all applicable local laws and provide subjects with information regarding the purpose, procedures, requirements, and restrictions of the study, along with any known risks and potential benefits associated with the IP, the available compensation, and the established provisions for maintaining confidentiality of personal, protected health information. Subjects will be told about the voluntary nature of participation in the study and must be provided with contact information for the appropriate individuals should questions or concerns arise during the study. The subject also must be told that their records may be accessed by appropriate authorities and Sponsor-designated personnel. The Investigator must keep the original, signed copy of the consent and must provide a duplicate copy to each subject according to local regulations. Following this study, the subject will return to their eye care professional for their routine eye care and contact lenses.

11 PROTOCOL AMENDMENT HISTORY

Version	Brief Description and Rationale
1	Initial Version of this document

Short Title:

**Statistical Analysis Plan
CLE383-C006**

Full Title:

**Statistical Analysis Plan
CLE383-C006 /
CLE383-C006**

Protocol Title: Clinical Comparison of Two Daily Disposable Soft Contact Lenses

Project Number: A01660

Protocol TDOC Number: TDOC-0055048

Author:

[REDACTED]

[REDACTED]

Template Version: Version 4.0

Approvals: See last page for electronic approvals

Job Notes:

This is the original (Version 1.0) Statistical Analysis Plan for this study. This version of the Statistical Analysis Plan is based on Version 1.0 of the study protocol.

Executive Summary:

Key Objective:

The primary objective of this study is to evaluate the overall performance of Daily Disposable (DD) T2 Soft Contact Lenses when compared to CooperVision® clariti® 1 day (Clariti 1 Day) lenses.

Decision Criteria for Study Success:

Decision criteria for study success are not applicable for this study.

Table of Contents

Statistical Analysis Plan CLE383-C006 1

Table of Contents 3

List of Tables..... 4

1 Study Objectives and Design..... 5

1.1 Study Objectives..... 5

1.2 Study Description 5

1.3 Randomization..... 6

1.4 Masking 6

1.5 Interim Analysis..... 6

2 Analysis Sets..... 6

2.1 Safety Analysis Set 6

█ [REDACTED] 6

4 Effectiveness Analysis Strategy..... 7

4.1 Effectiveness Endpoints 7

4.2 Effectiveness Hypotheses 8

4.3 Statistical Methods for Effectiveness Analyses..... 8

4.3.1 Primary Effectiveness Analyses 8

█ [REDACTED] 9

4.4 Multiplicity Strategy..... 9

4.5 Subgroup Analyses and Effect of Baseline Factors..... 9

4.6 Interim Analysis for Effectiveness 9

5 Safety Analysis Strategy 9

5.1 Safety Endpoints..... 9

5.2 Safety Hypotheses 10

5.3 Statistical Methods for Safety Analyses..... 10

5.3.1 Adverse Events..... 10

5.3.2 Biomicroscopy Findings/Slit Lamp Examination 10

5.3.3 Device Deficiencies..... 11

6 Analysis Strategy for Other Endpoints 11

█ [REDACTED] 11

8	References.....	11
9	Revision History.....	11
10	Appendix.....	12

List of Tables

Table 10-1	Overview of Study Plan.....	12
------------	-----------------------------	----

1 Study Objectives and Design

1.1 Study Objectives

PRIMARY OBJECTIVE

The primary objective of this study is to evaluate the overall performance of DD T2 lenses when compared to Clariti 1 Day lenses.

1.2 Study Description

Key components of the study are summarized in Table 1-1.

Table 1-1 Study Description Summary

Study Design	Prospective, randomized, bilateral crossover, double-masked
Study Population	Volunteer subjects aged 18 or over who are soft daily disposable contact lens wearers (excluding current Clariti 1 Day wearers), have at least 3 months of contact lens wearing experience, and who wear their habitual lenses at least 5 days per week and at least 8 hours per day. Target to complete: 20 Planned to enroll: ~22
Number of Sites	~1 US
Test Product	Daily Disposable T2 Soft Contact Lenses (DD T2)
Control Product	CooperVision® clariti® 1 day (Clariti 1 Day)
Duration of Treatment	~20 days total duration 
 • Test Product: 8 days (-1/+2 days) • Control Product: 8 days (-1/2 days)
Visits	Visit 1, Day 1: Baseline/Dispense Lens 1 Visit 2, Week 1 [Day 8 (-1/+2 Days)]: Follow-up Lens 1/Dispense Lens 2 Visit 3, Week 2 [Day 8 (-1/+ 2 Days)]: Follow-up Lens 2/Exit

1.3 Randomization

A member of the Randomization Programming group at Alcon who is not part of the study team will generate the randomized allocation schedule(s) for study lens sequence assignment. Randomization will be implemented in iMedidata Balance.

Qualifying subjects will be randomized in a 1:1 manner to one of 2 lens sequences consisting of the test lens and control lens as described below. For each sequence, subjects wear 1st lens then crossover to 2nd lens.

Sequence 1: DD T2/Clariti 1 Day

Sequence 2: Clariti 1 Day/DD T2

1.4 Masking

This study is double-masked.

1.5 Interim Analysis

[figure not shown]
There are no plans to conduct an interim analysis and no criteria by which the study would be terminated early based upon statistical determination

[figure not shown]
2 Analysis Sets

2.1 Safety Analysis Set

Safety analyses will be conducted using the safety analysis set on a treatment-emergent basis. As such, the safety analysis set will include all subjects/eyes exposed to any study lenses evaluated in this study. For treatment-emergent safety analyses, subjects/eyes will be categorized under the actual study lens exposed in the corresponding lens sequence.

Adverse events occurring from the time of informed consent but prior to first exposure to study lenses will be summarized in subject listings.

4 Effectiveness Analysis Strategy

This study defines one primary endpoint [REDACTED] The Safety Analysis Set will serve as the primary set for all effectiveness analyses.

Continuous variables will be summarized using the number of observations, mean, standard deviation, median, minimum, and maximum, as well as confidence intervals where applicable. Categorical variables will be summarized with counts and percentages from each category.

All data obtained in evaluable subjects/eyes will be included in the analysis. No imputation for missing values will be carried out for the primary analysis.

A listing of selected effectiveness data will also be provided.

[figure not shown]
4.1 Effectiveness Endpoints

[figure not shown]
Primary Endpoint

The primary endpoint is the subjective rating on overall quality of vision, collected binocularly on a scale of 1 (Poor) to 10 (Excellent) at the Day 8 Follow-up visits.

Secondary Endpoint

No secondary endpoint is defined for this study.

[figure not shown]

4.2 Effectiveness Hypotheses

Primary Effectiveness

No inferences are to be made on the primary effectiveness endpoint, therefore, no hypotheses are formulated.

4.3 Statistical Methods for Effectiveness Analyses

4.3.1 Primary Effectiveness Analyses

The subjective rating of Overall Quality of Vision will be summarized as both continuous and categorical. As a continuous variable, descriptive statistics as well as a two-sided 95% confidence interval for the mean of each study lens will be provided. As a categorical variable, counts and percentages will be provided for the following categories: 9-10, 7-8, 5-6, 3-4, 1-2.

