3.2 Trial Objective

The primary objective of this study is to evaluate the overall performance of DD T2 lenses when compared to Clariti 1 Day lenses.

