6.1 Subject Evaluability

The final subject evaluability will be determined prior to breaking the code for masked treatment sequence assignment and locking the database, based on the Deviations and Evaluability Plan.

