6.4.1.2 Analysis Methods

Descriptive statistics will be provided.

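### Optional low-cost improvement, not an error: the only visible objective compares two lenses in a crossover, but SAP 4.3.1 plans per-lens summaries and no within-subject difference

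*SAP*

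**What the plan says.** Protocol 3.2 states the primary objective as being to "evaluate the overall performance of DD T2 lenses when compared to Clariti 1 Day lenses"; SAP 1.1 repeats it. Protocol 6.4.2 says there is no secondary objective or endpoint.

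The design is a randomized two-sequence crossover. SAP 1.3 allocates 1:1 and says: "For each sequence, subjects wear 1st lens then crossover to 2nd lens". Under SAP 4.1 the endpoint is one binocular rating from 1 to 10 at each Day 8 follow-up, so a completer gives one rating per lens. SAP 1.2 sets the size: "Target to complete: 20 Planned to enroll: ~22".

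On analysis, Protocol 6.4.1.2 says only "Descriptive statistics will be provided". SAP 4.3.1 adds "a two-sided 95% confidence interval for the mean of each study lens will be provided" and counts in five rating bands. SAP section 4 lists the usual summaries for continuous variables, "as well as confidence intervals where applicable", and promises a listing of selected effectiveness data without saying which variables it will hold.

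Both documents state that no inference is made and no hypothesis is formulated for this endpoint (Protocol 6.4.1.1, SAP 4.2). The SAP executive summary says success criteria do not apply.

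**The concern.** The stated question is how one lens compares with the other, and the design pairs every subject with themselves. The planned primary output describes each lens separately and never forms the pair.

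Protocol 3.1 says the data are meant to inform product development, so readers of the report will compare the two lenses. They will have two means and two intervals, and can subtract the means. They cannot tell from that table how precisely the difference is estimated. If they treat the two summaries as independent groups, they ignore the pairing that the crossover was designed to give.

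What is at stake is the usefulness of the main table, not the validity of anything in it.

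**Working it through.** **Plan's own figure.** The visible text gives no SD, correlation, power or precision target, so there is nothing to reproduce.

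**Inputs.** From the documents: 20 completers (SAP 1.2), 1:1 allocation (SAP 1.3), hence 10 per sequence if balance holds; two-sided 95% intervals (SAP 4.3.1). Assumed: equal rating SD for both lenses of 1.0, 1.5 or 2.0, and within-subject correlation ρ of 0.3, 0.5 or 0.7.

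**Step 1: does the planned table fix the precision of the comparison?** The variance of the difference is SD₁² + SD₂² − 2ρ·SD₁·SD₂, and the planned summaries do not report ρ. A constructed example with 20 ratings per lens:

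- Lens A: two 10s, four 9s, six 8s, four 7s, two 6s, two 5s. Mean 154/20 = 7.70, SD 1.45, 95% CI 7.02 to 8.38.
- Lens B: one 10, three 9s, five 8s, six 7s, two 6s, two 5s, one 4. Mean 145/20 = 7.25, SD 1.52, 95% CI 6.54 to 7.96.

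The difference is 0.45 however the ratings are paired. Paired in rank order (ρ = 0.94), its 95% CI is 0.21 to 0.69. In a shuffled pairing (ρ = 0.11) it is −0.48 to 1.38. The planned table would be identical in both cases.

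**Step 2: size at the planned n.**

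- Per-lens half-width = t(0.975, 19) × SD/√20 = 2.093 × SD/4.472 = 0.468 × SD.
- SD of the difference = SD × √(2(1 − ρ)).
- Half-width for the difference, averaged equally over sequences = t(0.975, 18) × SD of the difference × ½√(1/10 + 1/10) = 2.101 × 0.2236 × SD of the difference.

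For SD 1.5 and ρ = 0.3: SD of the difference = 1.5 × 1.183 = 1.775, and 2.101 × 0.2236 × 1.775 = 0.834.

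| Assumed SD | Each lens | Difference, ρ = 0.3 | ρ = 0.5 | ρ = 0.7 |
|---|---|---|---|---|
| 1.0 | ±0.468 | ±0.556 | ±0.470 | ±0.364 |
| 1.5 | ±0.702 | ±0.834 | ±0.705 | ±0.546 |
| 2.0 | ±0.936 | ±1.112 | ±0.940 | ±0.728 |

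At SD 1.5 the range over ρ = 0.3 to 0.7 is 0.834/0.546 = 1.53-fold. With equal SDs and ρ not negative, a reader of the planned table could say only that the half-width is at most about √2 × 0.702 = 0.99 (0.997 on 18 df).

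**Step 3: when is the difference interval narrower than a per-lens interval?** When 2.101 × √(2(1 − ρ)) is below 2.093, that is, when ρ exceeds 1 − ½(2.093/2.101)² ≈ 0.504.

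**Step 4: cost of adjusting for period.** Relative to a simple paired interval on 19 df, the width ratio is 2.101/2.093 = 1.004 at 10:10. At 11:9 it is 1.009.

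**Step 5: does the interval hold up on a capped integer scale?** Simulation: bivariate normal latent ratings, SD 1.8, latent correlation 0.3, 0.5 or 0.7, rounded and clipped to 1–10, 10 per sequence, 40,000 runs per setting. For observed mean ratings of about 8.3 to 9.0, coverage is near 95% (about 94.8% to 95.3%). With one lens averaging about 9.7 to 9.9 and the other about 9.3, it falls to roughly 92% to 94.5%. If both lenses sit closer to 10 it can go lower: in the same model, observed means of 9.9 and 9.7 with latent correlation 0.7 gave about 90%.

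**The case against.** The strongest reply is that the plan does what it says. It disclaims inference, hypotheses, testing and success criteria, and per-lens summaries are consistent with that. This stands. A reader might infer that the primary analysis is wrong or invalid; the documents do not support that, because each per-lens interval is valid for its own lens mean and no planned conclusion depends on a difference.

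Four further points stand in part.

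- **The listing.** A reader might infer that the precision of the comparison is lost altogether. If the listing of selected effectiveness data includes this rating, each subject's pair could be recovered by hand for about 20 subjects. Its content is not stated, so this is possible, not assured.
- **The objective.** A reader might infer that this is the study's sole objective. It is the only visible one; text beside the primary endpoint and a SAP contents entry between 4.3.1 and 4.4 are redacted. SAP 4.3.1 itself reads as complete.
- **Missing ratings.** A reader might infer that the two lens means would come from different subjects. The SAP says "All data obtained in evaluable subjects/eyes will be included in the analysis", and Protocol 6.1 settles evaluability "based on the Deviations and Evaluability Plan", which is not available here. Nothing shows that the sets would differ, so the point does not rest on this.
- **Precision.** A reader might infer that pairing always gives a tighter interval than those planned. Below a correlation of about 0.5 it is wider than each per-lens interval.

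The descriptive character of the study does not count against the addition. The SAP already plans descriptive confidence intervals for this endpoint, and one for the difference, labelled as such, is no more inferential.

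**Conclusion.** The point holds as an optional, low-cost improvement. In a crossover whose visible objective is comparative, the planned summary table would show the difference only by subtraction and would not show its precision. At 20 completers and SD 1.5, one and the same per-lens half-width of ±0.70 is compatible with ±0.83 to ±0.55 for the difference over correlations 0.3 to 0.7. These sizes rest on assumed SDs and correlations, equal SDs for the two lenses, and 10 completers per sequence. That the planned summaries do not determine the precision of the difference needs none of those assumptions.

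**What to change.** Keep the per-lens summaries and add to SAP 4.3.1:

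> For evaluable subjects with a Day 8 follow-up rating on both lenses, the within-subject difference in overall quality of vision (DD T2 minus Clariti 1 Day) will be summarised by n, mean, SD, median, minimum and maximum, overall and by sequence. The main estimate is the mean difference averaged equally over the two sequences, with a two-sided 95% CI (pooled within-sequence SD, n1 + n2 − 2 df). The CI is descriptive, is not a hypothesis test, assumes no carryover, and is approximate for a bounded rating.

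Naming the main estimate matters because, with unequal sequences, it differs slightly from the raw mean difference. Protocol 6.4.1.2 is broad enough to cover the addition as it stands.

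Cost: one paragraph and one table, with no extra subjects, visits or data. Downsides:

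- The interval could be misread as a test, hence the label.
- Period adjustment widens it by 0.4% at 10:10 and 0.9% at 11:9.
- It undercovers somewhat if ratings cluster near 10.
- It assumes no carryover. Protocol 5.1.2 has Lens 2 inserted at the Lens 1 follow-up visit and no washout is described, but subtracting the two planned means makes the same assumption.
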